7.2 Rationale

The ABBVIE REGIMEN ± RBV for the treatment of CHC has been shown to be safe and effective in randomized controlled clinical trials with strict inclusion and exclusion criteria under well controlled conditions.

The ABBVIE REGIMEN is expected to be first IFN-free combination available in the Russian Federation for the treatment of CHC in 2015.

The rationale for this observational study is to determine how the efficacy and safety of the ABBVIE REGIMEN as demonstrated in pivotal trials translates into real world everyday clinical settings, evaluating its effectiveness. Whereas efficacy can be defined as a measure of the capacity of a treatment to produce the desired effect in a controlled environment, such as in a randomized controlled trial, effectiveness is 'the extent to which a drug achieves its intended effect in the usual clinical setting' [64]. Effectiveness trials typically have limited exclusion criteria and will involve the broader patient populations in routine clinical practice, treated per local label, which might include patients with heterogeneous compliance patterns and patients with significant comorbid conditions and could be used to model and disseminate best practices. Effectiveness research allows for external patient-, provider-, and system-level factors and can therefore be relevant for health-care decisions by both providers in practice and policy-makers [65].

This observational study is the first effectiveness research examining the ABBVIE REGIMEN ± RBV, used according to local label, under real world conditions in the Russian Federation in clinical practice patient population.

During the last decade when dual therapy with pegIFN plus RBV was standard of care for the treatment of CHC, management of patients and clinical outcome were improved following the discovery of predictive factors of virological response, often in observational studies with large data bases [66]. Thus treatment could be targeted to patients most likely to respond and futile treatment stopped in patients with a low likelihood of virological cure. HCV genotype and subtype, baseline viral load, fibrosis stage, age, treatment exposure and on-treatment virological response proved to be useful predictors for the eradication of HCV in everyday clinical practice [27]. More recently the discovery

of a genetic disposition of the Interleukin 28B (IL28B) single nucleotide polymorphism (SNP) contributed further to our understanding of virological responses to treatment [67]. For new interferon-free treatment regimens knowledge of predictive factors of virological response is extremely sparse and several of the now well established predictors of response were not initially identified through analyses of the development trials. This observational study may play an important part in bridging the data gaps and could help identify predictive factors of virological response in everyday clinical settings which were not detected in interventional trials and which could be used to further optimize treatment with the interferon-free ABBVIE REGIMEN in the future.

The label of the ABBVIE REGIMEN will vary according to HCV genotype/subtype and stage of liver disease. It is therefore relevant to understand the pattern of use and outcome in daily clinical practice. In addition, this study will provide data on the impact of adherence on treatment outcomes in everyday settings, which may help treating physicians to improve the management of patients under their care.

The aim of this observational study is to provide evidence of the effectiveness, patient reported outcome, work productivity and healthcare resource utilization of the ABBVIE REGIMEN \pm RBV in a real world setting across clinical practice patient populations.

8.0 Research Question and Objectives

8.1 Research Question

What is the effectiveness, patient reported outcome, work productivity and healthcare resource utilization of the interferon-free ABBVIE REGIMEN \pm RBV in patients with CHC in a real life setting across clinical practice patient populations?

8.2 Objectives

8.2.1 Primary Objective

1. To describe in routine clinical practice the effectiveness of the interferon-free ABBVIE REGIMEN \pm RBV in patients with CHC as evidenced by SVR12

8.2.2 Secondary Objectives

2. To provide real world evidence for predictive factors of virological response

3. To collect information on co-morbidities and concomitant medication in the Russian population
4. To describe the tolerability of the ABBVIE REGIMEN ± RBV
5. To document the effect of the ABBVIE REGIMEN ± RBV on PROs and work productivity in the Russian population
6. To determine the impact of the ABBVIE REGIMEN ± RBV on healthcare resource utilization

9.0 Research Methods

9.1 Study Design

This is a prospective, multi-center observational study in patients receiving the interferon-free ABBVIE REGIMEN with or without RBV. The prescription of a treatment regimen is at the discretion of the physician in accordance with local clinical practice and label, is made independently from this observational study and precedes the decision to offer the patient the opportunity to participate in this study.

Adult patients chronically infected with HCV, receiving the interferon-free ABBVIE REGIMEN will be offered the opportunity to participate in this study during a routine clinical visit at the participating sites.

[figure not shown]
After written informed consent has been obtained, patient data including demographic data, HCV disease characteristics, co-morbidities, co-medication, treatment details, and laboratory assessments as recorded in the patient's medical records (source documentation) will be documented in the electronic case report form (eCRF). Patients will be observed for the duration of the ABBVIE REGIMEN therapy and for up to 24 weeks after treatment completion. No patient identifiable information will be captured, a unique patient number will be automatically allocated by the web based eCRF system once the investigator or designee creates a new patient file.

This study is focusing on collecting real-world data. Follow-up visits, treatment, procedures and diagnostic methods will follow physicians' routine clinical practice. The observational study period entails the following data collection schemes, data documented will be those closest to the time windows as indicated in Figure 1:

- 12-week treatment regimen: four visits plus two interim data collection windows
- 24-week treatment regimen: four visits plus three interim data collection windows

This schedule is based on the anticipated regular follow-up for patients undergoing treatment for CHC.

Figure 1 - Study Flowchart

9.2 Setting

For overall research design and observational documentation schedule refer to Sections 9.1 and 9.4.1 as well as to Figure 1.

9.2.1 Target Population

Patients are eligible for observation in this cohort if the following applies:

- Treatment-naïve or -experienced adult male or female patients with confirmed CHC, genotype 1, receiving combination therapy with the interferon-free ABBVIE REGIMEN ± RBV according to standard of care and in line with the current local label
- If RBV is co-administered with the ABBVIE REGIMEN, it has been prescribed in line with the current local label (with special attention to contraception requirements and contraindication during pregnancy)
- Patients must voluntarily sign and date informed consent prior to inclusion into the study
- Patient must not be participating or intending to participate in a concurrent interventional therapeutic trial

Confidential Information

No use or disclose outside AbbVie is permitted without prior written authorization from AbbVie

Version 3.0 (22 Apr 2015) – country v 1.0 dated 26.06.2015

Page 22 of 61

9.2.2**Study Duration**

This is a prospective, observational study. The inclusion period will be approximately 8 months and the observational period of the study will be from baseline visit until 24 weeks post-treatment.

The observational period for patients receiving 12 weeks of ABBVIE REGIMEN will be max. 36 weeks (12 weeks treatment and 24 weeks post-treatment observation) and for patients receiving 24 weeks of ABBVIE REGIMEN the observational period will be max. 48 weeks (24 weeks treatment and 24 weeks post-treatment observation).

9.2.3**Termination Criteria**

For patients who terminate the ABBVIE REGIMEN prematurely for whatever reason the EoT eCRF page should be filled in and the reason for treatment discontinuation should be documented. If the reason for ABBVIE REGIMEN discontinuation is due to an SAE, the event must be reported to AbbVie within 24 hours of physician awareness (see Section 11.5).

If, in such patients, there is evidence of virological response during therapy or at EoT, the SVR12 and SVR24 pages should be completed if respective data is available.

9.2.4**Investigator Selection Criteria**

University centers and outpatient clinics qualified by training and experience in the management of patients with CHC will be selected to participate in this study. The AbbVie Affiliate Medical Director will ensure that sites participating in the study are representative of the medical practice in the country, have the ability to conduct the study and their availability of the target patient population. The type of the participating treating institute will be documented in the eCRF.

9.3 Variables

9.3.1 Primary Variable

- The percentage of patients achieving SVR12 (HCV RNA <50 IU/mL 12 weeks [i.e. ≥70 days] after the last actual dose of the ABBVIE REGIMEN)

9.3.2 Secondary Variables

- Co-morbidities and concomitant medication
- Serious and non-serious adverse events and pregnancy occurrences
- Questionnaires on PROs: EuroQol 5 dimension 5 level (EQ-5D-5L) questionnaire and work productivity and activity impairment (WPAI) questionnaire prior to treatment initiation, at EoT as well as 12 and 24 weeks after EoT
- PAM-13, PSP satisfaction and utilization questionnaires

9.4 Data Sources

Source documents are defined as original documents. The investigator will document patient data in his/her own patient files which will serve as source data for the study. Data are collected from the source documents for each patient in the study, consisting of medical records containing demographic data, medical, treatment and diagnostic documentation and laboratory assessments.

The investigator(s)/institution(s) will permit study-related monitoring, audits, independent ethics committee/- review board (IEC/IRB) review, and regulatory inspection(s), providing direct access to source data documents.

9.4.1 Data to be Documented

This observational study covers three documentation periods, see Figure 1. An overview on data to be collected throughout the study is summarized in **Table 2**.

After the patient has signed informed consent, the following data will be documented in the eCRF, if available from the patient charts based on assessments done in physicians' routine clinical practice.

Confidential Information

No use or disclose outside AbbVie is permitted without prior written authorization from AbbVie

Version 3.0 (22 Apr 2015) – country v 1.0 dated 26.06.2015

Page 24 of 61

9.4.1.1 Inclusion Documentation

The following will be documented:

- Demographic information
 - Interleukin 28B (IL28B) genotypes
- CHC disease characteristics
 - Year of diagnosis and mode of infection
 - Stage of liver fibrosis
- CHC treatment history
 - Naïve or experienced
 - If experienced, most recent prior therapy and outcome
- Relevant medical history, co-morbidities and co-infections
- Concomitant medication, see 9.4.1.5
- ABBVIE REGIMEN ± RBV
- Laboratory data

Key clinical chemistry	Remarks
▪ ALT (alanine-aminotransferase)	including upper limit of normal (ULN),
▪ AST (aspartate-aminotransferase)	including ULN, AST to platelet ratio index (APRI) and Fibrosis-4 Score/Index (FIB-4)* will be calculated
▪ γ-GT (gamma-glutamyltransferase)	
▪ Total bilirubin	
▪ Albumin	
▪ Creatinine	creatinine clearance [#] will be calculated
▪ AFP	
Key hematology	
▪ Hb (Hemoglobin)	
▪ Platelets	
▪ Prothrombin time	or international normalized ratio (INR)
Virology	
▪ HCV genotype and subtype	
▪ HCV RNA	quantitative/ qualitative HCV RNA by polymerase chain reaction (PCR) test, see 9.4.1.4
HIV-infected patients only	
▪ CD 4 count (cluster of differentiation 4)	most recent assessment
▪ HIV RNA	in copies/mL

*derived from patient's age, ALT, AST and platelets

[#]by Cockcroft-Gault-Formula based on creatinine, gender, age and weight

Confidential Information

No use or disclose outside AbbVie is permitted without prior written authorization from AbbVie

Version 3.0 (22 Apr 2015) – country v 1.0 dated 26.06.2015

Page 25 of 61

- Patient questionnaires, see table 2 and 9.4.1.6
- PAM-13
- Treatment related health care resource utilization

9.4.1.2 During Treatment Documentation

Follow-up visits are scheduled by the physician per routine clinical practice. Likewise treatment, procedures and diagnostic methods will follow physicians' routine clinical practice.

The following will be documented:

- Laboratory data

Key clinical chemistry	Remarks
▪ ALT	including ULN
▪ AST	including ULN, APRI and FIB-4 will be calculated
▪ γ-GT	
▪ Total bilirubin	
▪ Creatinine	creatinine clearance will be calculated
Key hematology	
▪ Hb	
▪ Platelets	
Virology	
▪ HCV RNA	quantitative/ qualitative HCV RNA PCR test, see 9.4.1.4
HIV-infected patients only	
▪ CD 4 count	most recent assessment
▪ HIV RNA	in copies/mL

- Concomitant medication, see 9.4.1.5
- Adherence to ABBVIE REGIMEN ± RBV (ABBVIE REGIMEN - % of target dose taken and RBV Y/N)
- Tolerability (sAEs and AEs, see 11.5) and pregnancies (see 11.6)
- Patient questionnaires see 9.4.1.6
- PSP satisfaction and utilization questionnaires; PAM-13
- Treatment related health care resource utilization

9.4.1.3 Post-Treatment Documentation

Follow-up visits are scheduled by the physician per routine clinical practice. Likewise treatment, procedures and diagnostic methods will follow physicians' routine clinical practice.

Confidential Information

No use or disclose outside AbbVie is permitted without prior written authorization from AbbVie

Version 3.0 (22 Apr 2015) – country v 1.0 dated 26.06.2015

Page 26 of 61

The following will be documented:

- Laboratory data

Key clinical chemistry	Remarks
▪ ALT	including ULN
▪ AST	including ULN, APRI and FIB-4, will be calculated
▪ γ-GT	
▪ Total bilirubin	
▪ Albumin	
▪ Creatinine	creatinine clearance will be calculated
Key hematology	
▪ Hb	
▪ Platelets	
▪ Prothrombin time	or INR
Virology	
▪ HCV RNA	quantitative/ qualitative HCV RNA PCR test, see 9.4.1.4
HIV-infected patients only	
▪ CD 4 count	most recent assessment
▪ HIV RNA	in copies/mL

- Tolerability (sAEs, see 11.4) and pregnancies (see 11.6)
- Patient questionnaires see 9.4.1.6
- PSP Satisfaction and utilization questionnaires

Confidential Information

No use or disclose outside AbbVie is permitted without prior written authorization from AbbVie

Version 3.0 (22 Apr 2015) – country v 1.0 dated 26.06.2015

Page 27 of 61

Table 2 - Data Documentation Schedule

Assessment/ Procedure (only available data to be collected; no diagnostic or monitoring procedures to be applied to the patients apart from those of routine clinical practice)	Baseline	Treatment Period			Post-treatment (PT) Period		
		On-treatment visits	Mid treatment visit for pts receiving 24 weeks of therapy	EoT ^b	Early PT visit	SVR 12 visit	SVR 24 visit
Informed Consent	X ^a						
Demographic information	X						
IL28B	X						
Relevant CHC disease characteristics	X						
Liver fibrosis stage	X						
CHC treatment history	X						
HCV genotype and subtype	X						
HCV RNA samples	X	X	X	X	X	X	X
Clinical chemistry and hematology	X	X	X	X	X	X	X
ABBVIE REGIMEN initiation documentation	X						
ABBVIE REGIMEN adherence		X	X	X			
Concomitant medication	X	X	X	X			
Relevant medical history, co-morbidities	X						
sAE, AE and pregnancy reporting	X	X	X	X	X ^c	X ^d	X ^d
For patients receiving RBV: Evidence, in accordance with local label, that female patient or female partner of male patient is not pregnant	X						
Patient questionnaires – WPAI, EQ5D-5L	X			X		X	X
Patient questionnaires – PAM-13	X			X			
PSP evaluation		X	X	X	X	X	
Health care resource utilization	X	X	X	X			

Abbreviations: EoT = End of Treatment (at Week 12 or 24 or at premature discontinuation),

PT = Post-Treatment

a Written patient authorization or informed consent must be obtained before any data documentation in the eCRF

b Patients who prematurely discontinue should return to the site to document EoT data

c Tolerability documentation until PT week 4

d Pregnancy reporting for patients treated with DAA plus RBV

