9.7.7 Tolerability Analysis

All tolerability variables will be summarized using descriptive statistical methods for the SP stratified by type of combination treatment and scheduled treatment duration.

All SAEs, non-serious AEs and pregnancy occurrences are to be reported for patients included in the study (see Section 11.0 and 9.2.3). AEs will be coded using MedDRA. The number and percentage of patients with treatment-emergent AEs (i.e. any reported event that begins or worsens in severity after initiation of study drug through 30 days post-study drug dosing) will be tabulated by primary MedDRA SOC and PT. Corresponding summary tables will be provided for all serious treatment-emergent AEs. The tabulation of the number of patients with treatment-emergent AEs by severity and relationship to study drug will also be provided. Patients reporting more than one AE for a given MedDRA PT will be counted only once for that term using the most severe incident for the severity summary table and the most related for the relationship summary table. Patients reporting more than one type of event within a SOC will be counted only once for that SOC.

Additional details of the analysis of AEs will be specified in the SAP.

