11.4 Serious Adverse Event Collection Period

SAEs will be reported to AbbVie from the time the physician obtains the informed consent until 30 days or 5 half-lives following the intake of the last dose of physician-prescribed treatment.

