### **5.2 Windowing conventions**

Due to exploratory nature of the study all interim time-points will be separated into visits in the analysis stage. The most detailed possible situation is:

- on-treatment Week 4 from 15 to 42 study days;
- on-treatment Week 8 from 43 to 70 study days;
- on-treatment Week 12 from 71 to 98 study days;
- on-treatment Week 16 from 99 to 126 study days;
- post-treatment Week 4 from 15 to 56 days post EoT.

Table 5.1 describes assignment of time point windows to the following data for purposes of effectiveness, safety and tolerability analyses.

Table 5.1 – Analysis time windows

| Time point             | Time Window  |                        |
|------------------------|--|------------------------|
|                        | 12 weeks treatment   | 24 weeks treatment     |
| Baseline        | Last value prior to start of study treatment (i.e. $\leq$ study day 1) |                        |
| EoT | Last value between   |                        |
|                        | 56 and 98 study days   | 140 and 182 study days |
| SVR12           | Last value between 57 and 112 days post the study day of last dose     |                        |
| SVR24           | Last value between 141 and 196 days post the study day of last dose    |                        |

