### 11.2 Adverse Events

Only treatment-emergent adverse events will be analyzed.

*Treatment-emergent AE* is any reported event that begins or worsens in severity after initiation of study drug through 30 days post-study drug dosing.

All analyzed AEs will be coded using the MedDRA version 20.0 (or further updating) and tabulated in the report with grouping by primary system organ class (SOC) and preferred term (PT).

The frequency of a specific AE occurrence will be presented by the proportion of patients with this AE emergence as well as the total number of episodes this AE for a diagnosis.

The following tables with descriptive statistics in accordance with section 7.1 will be presented:

- all AE / SAE;
- AE / SAE by severity;
- AE / SAE by relationship to the study drug.

Tables of AE/SAE by severity (relationship to the study drug) will be prepared using the following rules. Each SOC / PT category will include only the AEs with the highest severity (relationship to the drug) in each patient, while in the Total category all AEs of this patient will be considered. At the same time, each patient will be counted only once with highest severity (relationship to the study drug) in each SOC and each PT level as well as Total level.

Also all AEs will be presented in listings. Additional listings for unintended medication errors will be provided.

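### Post-treatment collection rules for non-serious adverse events conflict with one another and with the 30-day treatment-emergent window that the analysis reports

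*Protocol*

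**What the plan says.** **Collection on treatment.** Protocol 9.4.1.2 documents both kinds of event: "Tolerability (sAEs and AEs, see 11.5) and pregnancies (see 11.6".

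**Collection after treatment.** The protocol gives three different accounts.
- Section 9.4.1.3 lists "Tolerability (sAEs, see 11.4) and pregnancies (see 11.6". Non-serious events are absent, and the cross-reference has moved from 11.5 to 11.4. Section 11.4 covers serious events only, "until 30 days or 5 half-lives following the intake of the last dose of physician-prescribed treatment".
- Table 2 has a row headed "sAE, AE and pregnancy reporting" that is marked at the early post-treatment visit, with the footnote "c Tolerability documentation until PT week 4". At the SVR12 and SVR24 visits, footnote d restricts the row to pregnancy reporting for patients treated with ribavirin.
- Section 11.5 tells physicians to report non-serious events through the eCRF, and 9.7.7 says that serious and non-serious events are to be reported. Neither gives an end date.

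**Analysis.** Protocol 9.7.7 defines a treatment-emergent event as "any reported event that begins or worsens in severity after initiation of study drug through 30 days post-study drug dosing", and SAP 11.2 repeats the definition. The SAP adds: "Only treatment-emergent adverse events will be analyzed". Results are split by scheduled combination and duration (Protocol 9.7.7, SAP 11).

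**The concern.** The analysis window closes at day 30 for every event, serious or not. No collection rule for non-serious events closes at day 30. One rule excludes them after the last dose, one stops at week 4, and one has no stop. Two sites could both follow the protocol in good faith and record different things.

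The planned outputs would not show this. SAP 7.4 pools all centers, SAP 8.2 presents no protocol deviations, and the adverse event shells (Tables 4.2.1 to 4.4.2) do not separate on-treatment from post-dose events. A reader could not tell an absence of events from an absence of collection. Describing tolerability is a secondary objective (Protocol 8.2.2), and these tables are its main output.

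**Working it through.** The plan states no figure on this point, so there is none to reproduce. The check compares collection days with analysis days.

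**Inputs**
- Treatment length: 12 weeks = 84 days, or 24 weeks = 168 days (Protocol 9.2.2).
- Treatment-emergent window: treatment plus 30 days (Protocol 9.7.7, SAP 11.2).
- Post-treatment week 4: day 28, or day 29 by the label in Protocol Table 4.
- Daily hazard of a first non-serious event: not in the documents. Assumed range 0.001 to 0.01 per patient-day, constant on and after treatment and equal in both regimens.

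**Step 1: days not covered if sites follow 9.4.1.3.** Share = 30/(T + 30).
- 12 weeks: 30/(84 + 30) = 30/114 = 26.3%. Collected: 84/114 = 73.7%.
- 24 weeks: 30/(168 + 30) = 30/198 = 15.2%. Collected: 168/198 = 84.8%.

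**Step 2: days not covered if sites follow Table 2.** The gap is 30 − 28 = 2 days or 30 − 29 = 1 day.
- 12 weeks: 1/114 to 2/114 = 0.9% to 1.8%.
- 24 weeks: 1/198 to 2/198 = 0.5% to 1.0%.

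**Step 3: illustration in patients, under the assumed hazard λ.** Proportion with at least one event over d days = 1 − exp(−λd). The table compares the full window (T + 30) with treatment days only (T), as under 9.4.1.3. Losses are computed before rounding.

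| λ per day | 12 weeks: full, collected (%) | Loss, points (relative) | 24 weeks: full, collected (%) | Loss, points (relative) |
|---|---|---|---|---|
| 0.001 | 10.77, 8.06 | 2.72 (25.2%) | 17.96, 15.46 | 2.50 (13.9%) |
| 0.002 | 20.39, 15.46 | 4.92 (24.1%) | 32.70, 28.54 | 4.16 (12.7%) |
| 0.005 | 43.45, 34.30 | 9.15 (21.1%) | 62.84, 56.83 | 6.01 (9.6%) |
| 0.01 | 68.02, 56.83 | 11.19 (16.5%) | 86.19, 81.36 | 4.83 (5.6%) |

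Under Table 2 with a 2-day gap, the loss over the same hazards is at most about 0.65 points.

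**Step 4: the post-dose rate alone.** The post-dose window is 30 days in both regimens. At λ = 0.005, 28 days give 13.06% and 30 days give 13.93%, whatever the treatment length. At equal hazard, the loss in the post-dose rate does not depend on regimen length.

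**Step 5: serious events.** If the 30-day limb of 11.4 governs, collection matches the analysis and nothing is lost. The section does not say which of its two limbs applies, and footnote c ends earlier.

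**The case against.** The strongest reply is that 9.4.1.3 is one bullet against three other places. Table 2, 11.5 and 9.7.7 all call for non-serious events, so zero capture requires a site to follow the bullet and ignore the rest. This stands in part: an undercount is possible, not established. It does not remove the conflict. The cross-reference in 9.4.1.3 changes along with the wording, so a serious-only reading is reasonable, and 11.5 and 9.7.7 add an open-ended rule without settling the end date.

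Two stronger readings are tempting, and the documents do not support them.
- A reader might infer that an early post-treatment visit on day 15 leaves days 16 to 30 without any collection. The range behind that ("post-treatment Week 4 from 15 to 56 days post EoT") assigns data to time points at analysis. It is not a visit window. The collection windows are in Protocol Figure 1, which is not reproduced in the text available. Reporting under 11.5 is also triggered by the event and not tied to a visit.
- A reader might infer that post-treatment rates are distorted by regimen length. Step 4 shows otherwise. Only the overall treatment-emergent rate loses a different share of days. The number of 24-week patients is also unknown: the SAP shells name only 12-week columns and leave the others open.

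Two further objections stand. Shares of days are not shares of events. Protocol 7.1 links many events to ribavirin and reports bilirubin elevations peaking by week 1, so events may cluster early and the constant-hazard losses may be too large. The SAP was also written from Protocol version 4.0 (11 July 2017) and CRF version 2.0 (25 May 2016), whereas the protocol reviewed is version 3.0 with a 2015 country version. The later documents may already resolve the conflict.

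**Conclusion.** The conflict is real in the documents supplied, and the SAP does not resolve it. If sites followed 9.4.1.3, non-serious events are missing for 26% of the treatment-emergent window's days in 12-week patients and 15% in 24-week patients, and the overall treatment-emergent rate can be undercounted. Under the assumed hazards, that is 2.7 to 11.2 points for 12 weeks and 2.5 to 6.0 points for 24 weeks. If sites followed Table 2, the gap is 1 to 2 days and negligible.

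These sizes rest on which passage sites used and on a constant hazard, neither of which the documents establish. Serious events are not affected if the 30-day limb of 11.4 applies. The primary endpoint is untouched. The point should be corrected because it determines which events enter the tolerability tables.

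**What to change.** First check whether Protocol version 4.0 and CRF version 2.0, which the SAP cites, already settle the matter.

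If they do not, use one collection period for serious and non-serious events that matches the 30-day treatment-emergent definition:
- In 9.4.1.3, list serious and non-serious events and refer to both 11.4 and 11.5.
- In Table 2 footnote c, replace post-treatment week 4 with 30 days after the last dose.
- State the period for non-serious events in 11.4 and 11.5, and say in 11.4 how the two limbs relate.

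Data collection was scheduled to end in August 2017 (Protocol 6.0) and SAP 2.0 is dated February 2018, so protocol edits may come too late to change the data. SAP section 2 permits revision before database soft lock. In that case, tabulate non-serious events separately for the on-treatment and post-dose periods, label the post-dose part as possibly incomplete, and report serious events through 30 days. Do not restrict non-serious events to the on-treatment period, because that would discard post-dose events recorded under Table 2 or 11.5.

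The cost is slightly more event entry at sites, or one additional split in the adverse event tables.
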